- **Data Management.** In the initial 3 months, data management procedures will be developed and implemented. Data entry and quality assurance will be ongoing during enrollment, with validation and double-entry procedures in place to ensure accurate data entry. Study staff will be trained to limit missing data by checking questionnaires

immediately and prompting for additional response and re-contacting participants if necessary. Study staff will attempt to collect all post-randomization data regardless of treatment attrition.

- **Statistical Analysis.** Data analysis will occur in a staged approach, moving from initial descriptive analyses to hypothesis tests. Descriptive statistics and plots will summarize and assess distributional properties of key variables. Randomized groups will be compared on baseline demographic and clinical variables using analysis of variance, 2, or Wilcoxon-rank sum tests. Any baseline variables potentially confounded with treatment condition will be incorporated in the primary analyses as covariates. Outliers will be assessed and variables whose distributions depart significantly from normality will be transformed.

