- **Missing Data.** The primary outcome will be tested using an intent-to-treat framework. If, the extent of missing data is small and the data appear to be consistent with a missing-at-random model (MAR) [84], then the maximum likelihood analysis using all randomized cases and the observed data is an appropriate method for handling the missing data [85]. In the MAR model the missingness can be a function of the observed covariates and observed outcomes. If the missingness is related to the unobserved outcome, then the missing values are considered missing not at random (MNAR). However, the MAR assumption has been shown to be plausible even in studies such as substance abuse in adolescents [86]. The critical element when conducting MAR-based analyses is to include covariates related to the missingness in the statistical model [87]. As a check on the sensitivity of our conclusions to the assumption that the missing data are MAR we will conduct pattern-mixture modeling, which is appropriate with data is likely MNAR [88, 89]. In these models participants are categorized into groups based on patterns of missing data over time. Missing data pattern groups are then included as covariates in the statistical model and the effect of missing data on parameter estimates can be determined. Parameter estimates can be averaged over the missing patterns to adjust for biased estimates.

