2) To minimize the risk of patient discomfort, confidentiality will be stressed, participants will be offered breaks as needed, they will be informed that they have the right to refuse to answer questions or to terminate their participation in the study at any time without prejudice, and everyone who interacts with participants will be trained and supervised. Clinical staff will be available at each location if immediate in-person evaluation is required for medical or mental health issues.

3) and 4) To minimize the risk of patients becoming more anxious or depressed or increase drinking, every patient will be given a 24-hour contact phone number to call in the event of increased symptoms. During each assessment, the independent evaluator (IE) will assess for any major changes in health (e.g., overnight hospitalizations), possible adverse events, suicidal ideation, and general well-being. Study clinicians, during medication and psychotherapy visits, will assess for clinical worsening as part of the session protocols. If worsening symptoms are detected at any visit, a study clinician will be available to evaluate the patient and refer to appropriate treatment if needed. When in doubt, the decision whether continued participation in the study is safe and clinically warranted will always be on the side of patient safety. If a therapist or assessor identifies worsening substance use, the study investigators will evaluate whether best clinical care indicates a need for continuation in the study or more intensive SUD treatment. Participants will complete the Substance Use Inventory (SUI) at each session which will show worsening substance use. Therapists will be trained to contact the PI if a participant reports three or more days per week of alcohol use with more than four standard drinks or three or more days of illicit drug use in a week. If more intensive treatment is appropriate, we will assist the participant in obtaining the appropriate treatment. If the treatment is counter to study criteria, then we will discontinue the participant from the study following a final evaluation.

Adverse events, including those unlikely to be the result of participation in the research (e.g., hospitalization due to an automobile accident), will be monitored at every study contact, including medication, psychotherapy and assessment visits. They will be reported to the appropriate human subjects committees as per policy.

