There is always a risk associated with the management of patients with AUD or PTSD that they will develop suicidality. This risk will be carefully mitigated by the systematic and careful assessment of suicidality throughout the protocol. This will be carefully done via the assessment measures to be completed by the participants, in-session assessments made by the therapists, and through comprehensive suicide risk assessments that are part of standard VA care. Participants who develop suicidality will be evaluated by a study clinician and investigators to determine whether continued participation in the study is safe and clinically warranted. If the study personnel and participant feel that treatment not allowed in the protocol is indicated (e.g., a different form of medication or psychotherapy, or hospitalization), an endpoint evaluation will be done, the participant will be discontinued from the study, and the participant will be referred for appropriate treatment.

5) Participants will be informed of the risks associated with the use of Topiramate, including all clinically significant warnings provided by the manufacturer in the medication package insert. This includes all current warnings and cautions in the most recent FDA guidelines dated May 2019 [95]. Given our frequent monitoring and standardized assessment of mood changes, we are already in compliance with the FDA's recommendation to monitor for this potentially rare adverse event. Participants will be informed that, as with any drug, Topiramate administration may involve other risks that are not known at the present time. If the study staff learns of any new possible risk or side effects of this drug, participants will be notified immediately. Participants will be informed that their condition may remain the same or deteriorate due to an ineffective treatment. They will also be informed of the availability of alternative treatments to facilitate alcohol use reduction. Participants will be told that if, in the opinion of the doctor, there are problems caused by their participation in the study that make it unwise for the participant to continue, their participation will be stopped. Patients who are discontinued from the study for any reason will be given a referral for further treatment if indicated.

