All eligible participants will receive a laboratory diagnostic evaluation consisting of a chemistry panel, complete blood count, liver function tests (LFTs), urine toxicology screen and pregnancy test during their screening and/or randomization appointments so that participants with any illnesses that might adversely be affected by their participation in the trial will be excluded.

6) The risks of simple venipuncture commonly include the occurrence of discomfort and/or bruising at the site of the puncture. Less commonly, fainting, the formation of a small blood clots or swelling of the vein and surrounding tissue, or bleeding from the puncture site may occur.

There could be infection at the site where the blood was drawn. All blood draws will occur at the VA lab by certified professionals.

Additional safety measures are as follows: 1) we will recruit individuals with AUD/PTSD who are seeking treatment to reduce alcohol use and symptoms; 2) a careful intake assessment will be conducted and patients in need of immediate psychiatric treatment for severe depression or other conditions will not be enrolled and provided referrals; 3) our team consists of clinicians with extensive experience in the treatment of patients with AUD and PTSD; 4) study therapists will review all active cases weekly with the PI and therapy supervisor, and all members of the research team will immediately communicate any health or psychiatric-related problems to the PIs who will ensure that necessary safety steps are implemented; and 5) participants who are discontinued from the study will be scheduled for a final evaluation within one week and given appropriate treatment referrals. Participants discontinued due to a serious adverse event will be followed clinically by medical staff until the adverse event is resolved or becomes stable. Reasons for discontinuation and referrals made will be documented in the participants' casebooks.

Psychiatric Emergencies

If exacerbation of psychological symptoms occurs, members of the research team will discontinue assessment and assist the subject to access care.

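### Section 15 takes some participants out of the study after a final evaluation, and the protocol leaves unclear whether their later heavy-drinking outcomes are still collected

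*Combined protocol and SAP*

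**What the plan says.** Section 15 (Risk Management) describes leaving the study in three places.

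- **Items 3) and 4), worsening substance use.** Therapists are trained to "contact the PI if a participant reports three or more days per week of alcohol use with more than four standard drinks"; a similar frequency of illicit drug use also prompts contact. When worsening use is identified, the investigators evaluate "whether best clinical care indicates a need for continuation in the study or more intensive SUD treatment". The rule that follows is: "If the treatment is counter to study criteria, then we will discontinue the participant from the study following a final evaluation".
- **Suicidality.** If treatment outside the protocol is thought to be indicated, "an endpoint evaluation will be done, the participant will be discontinued from the study, and the participant will be referred for appropriate treatment".
- **Additional safety measures, any reason.** Here "participants who are discontinued from the study will be scheduled for a final evaluation within one week", with referrals. Clinical follow-up after a serious adverse event continues until it resolves or is stable, and reasons for discontinuation are documented.

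The statistical part of Section 9 points the other way. Under Data Management: "Study staff will attempt to collect all post-randomization data regardless of treatment attrition". Under Missing Data: "The primary outcome will be tested using an intent-to-treat framework". The planned sensitivity analysis is also there: "As a check on the sensitivity of our conclusions to the assumption that the missing data are MAR we will conduct pattern-mixture modeling".

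Section 9 (Design) and its COVID-19 Procedures date the post-treatment, 3- and 6-month assessments from completion of treatment. Section 9 (Phone, mail, and Telehealth Appointments) and the COVID-19 Procedures allow assessments to be done remotely.

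**The concern.** An intent-to-treat comparison needs outcomes on everyone randomized, including those whose care changes. A final or endpoint evaluation, followed by discontinuation from the study, reads naturally as the last research contact. The Data Management sentence refers to attrition from treatment. It does not mention discontinuation from the study, and no visible passage says which text governs when both apply.

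The substance-use route deserves particular attention because it is related to the primary outcome. If people leave partly because they are drinking more, and PHDD is then not collected, missingness can depend on the outcome. Likelihood-based analysis handles this well only to the extent that what drove the exit is in the model.

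**Working it through.** **Step 1. The three exit texts side by side.**

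| Section 15 text | Trigger | Last contact described | Related to PHDD? |
|---|---|---|---|
| Items 3) and 4) | Worsening substance use, more intensive treatment judged appropriate, and that treatment conflicts with study criteria | Final evaluation | Yes |
| Suicidality | Treatment outside the protocol thought to be indicated | Endpoint evaluation | Not by its definition |
| Additional safety measures | Any reason | Final evaluation within one week | Not by its definition |

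**Step 2. Does another passage keep the later assessments?** The Data Management sentence may, if treatment attrition is read broadly. Section 9.9 describes following ongoing adverse events after withdrawal, which is safety follow-up and not outcome assessment. For people who need treatment during the follow-up phase, Section 9.9 speaks of referral, not of discontinuation. The gap therefore mainly concerns exits during the 16-week treatment period.

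**Step 3. What is lost on the literal reading.** PHDD is scheduled at four points: baseline, post-treatment, 3 months and 6 months. A participant who exits during treatment keeps baseline, so 4 − 1 = 3 scheduled values are missing. Section 9.8 uses the Timeline Follow-back at all assessment points. If it is given at the final evaluation, drinking up to exit may be captured, but not the later periods. Because the scheduled dates count from treatment completion, someone who stops early has no explicit dates even if staff try to follow the Data Management sentence.

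**Step 4. What the analysis can do.** The Primary Aim Analysis models PHDD at the four points by maximum likelihood. As described, it does not contain the session-level Substance Use Inventory reports that would reveal worsening use. The Missing Data section calls for covariates related to missingness, without naming them, and for pattern-mixture modeling. The latter groups participants by pattern of missing data, not by reason for exit. Both help in part; neither replaces values that were never collected.

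**Step 5. Power, for scale only.** Inputs from Section 9 (Power analysis) and Section 10: effect size d = 0.406, one-tailed test, 60 per arm. Alpha is not stated; 0.05 is assumed. Two-sample t-test with n per arm: noncentrality = d × √(n/2), with 2n − 2 degrees of freedom.

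- The protocol's figure, n = 60: 0.406 × √30 = 2.224, power 71.4%. The normal approximation gives 71.9%, which matches the stated 72%. The 192 participants for a two-tailed test, and the 80% two-tailed power at an effect of 0.516, also reproduce.
- Assumed 5% loss in both arms, n = 57: 0.406 × √28.5 = 2.167, power 69.5%.
- Assumed 10% loss in both arms, n = 54: 0.406 × √27 = 2.110, power 67.4%.

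The change from no loss to 10% loss is 71.4 − 67.4 = 4.0 percentage points. The loss rates are not from the documents, and none of the loss is shown to come from the Section 15 routes. The Power analysis states no allowance for missing outcomes, but it expects the repeated-measures model to have more power than this t-test.

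**The case against.** The strongest reply is that Data Management is the rule on data and Section 15 is the rule on care. On that reading there is no conflict: Section 15 never says in terms that outcome assessments stop, and the plan already asks for all data after randomization. This reading is available, so a flat contradiction, which a reader might infer, is not supported. What remains is that no visible passage says so, and the terms used at exit suggest the opposite to the staff who must act on them. The consent pages were not available, so a statement there cannot be excluded.

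Second, the drinking-related route is narrow. A reader might infer that heavy drinking removes people from the study. It does not: the drinking threshold prompts contact with the PI and is not a discontinuation rule. Exit also requires treatment that conflicts with study criteria, and the criteria in Section 10 bar little of this kind, chiefly current trauma-focused psychotherapy and an unstable dose of addiction medication. Section 9 (Standard Pharmacotherapy) and Section 9.8 expect continuing participants to receive other treatment and ask about inpatient stays. This stands, and it limits how many exits to expect.

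Third, the lack of explicit dates affects everyone who stops early, and a planned 16-week end can be inferred. That is fair; it makes the dating easy to settle.

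Fourth, the safety texts ask whether continued participation is appropriate, so an instruction to keep assessing could intrude on that judgement. This also stands, and the remedy must leave that decision to the clinicians.

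**Conclusion.** The point holds as an unclear instruction with a possible cost to the primary outcome. Followed literally, Section 15 ends PHDD collection for some randomized participants, and one of its routes is related to PHDD. Whether data would actually be lost depends on which reading staff adopt.

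The number of such exits is not given, so neither the size nor the direction of any bias can be computed; it may be small. A reader might infer that the treatment effect would be pulled toward no difference. That needs assumptions about exit rates by arm, and about how closely exit tracks later drinking, that the documents do not supply. A reader might also infer that the early final evaluation would stand in for the post-treatment value; no passage proposes this, though none rules it out.

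The power figures (71% with no loss, 67% at an assumed 10% loss) show scale only. The case for acting is that collecting the outcomes is inexpensive, while lost values cannot be recovered in analysis.

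**What to change.** Reconcile Section 15 with Section 9 (Data Management) for data collection only, and leave every clinical and safety rule as it is.

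1. State that discontinuation under Section 15 does not by itself end outcome assessment.
2. State that these participants are invited to the post-treatment, 3- and 6-month assessments, by phone or telehealth as Section 9 already allows, unless they withdraw consent or the study clinicians judge further assessment contact inappropriate.
3. Date those assessments from the planned end of the 16-week treatment period.
4. Keep the early final evaluation as a separate, dated record and do not use it as the scheduled post-treatment value.

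The cost is a short amendment and a few additional remote assessments. Some participants will decline or should not be contacted, so some data will still be missing and the planned sensitivity analysis is still needed.

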95. U. S. Food and Drug Administration. (2019, May). Medication Guide and Full Prescribing Information for TOPAMAX (topiramate). (Reference ID: 4426133). Retrieved from https://www.accessdata.fda.gov/drugsatfda_docs/label/2019/020505s060,020844s051lbl.pdf

Section 23 - Sponsors and Collaborators

23) Clarify any industry financial or other support (e.g., NIH funds the study or Company X provides the assay kits). Identify non-VASDHS Research collaborators and their role in this protocol, including whether or not they have access to subjects or identified data.

[name] from the UCSD School of Medicine will provide statistical support. He will not have access to identifiable data.

If genotyping is conducted outside the VA it will be via approved VA vendors for this service with an MTA. DNA extraction will be conducted by CFAR, a VA affiliated core.

Section 24 - Biological Materials Transfer Agreement (BMTA)

24) Describe what material is transferred, the persons/institutions that send and receive the material, and the status of the BMTA for this purpose. (see ? for further guidance)

The material to be transferred is DNA from saliva samples collected under this protocol. If

genotyping is conducted outside the VA it will be via approved VA vendors for this service with an MTA. DNA extraction will be conducted by CFAR, a VA affiliated core.

Section 25 - Impact on Clinical Services

25) Which VA Clinical Services participate in the performance of the project? (NOTE: All clinical trials and any use of clinical services will require project review and approval by the Office of Research Agreements Management (ORAM) to assure availability of those clinical resources. Prior discussion with the appropriate clinical service chief is strongly encouraged)

Check all that apply

- Pharmacy
- Laboratory
- Cardiology
- Radiology
- Nursing
- Nuclear Medicine
- MAS (Charts)
- Other (list below)

List others here

Section 27 - Protocol Attachments

If there is any material, such as tables or figures, that are referenced in the protocol text above but not pasted into the protocol application these can be attached in the Submission form along with other documents such as Consents and HIPAA Authorizations. press **Save and Continue**

Section 28 - Protocol Association to New or Existing Project

28) Is this a new R&D Project?. Before you go on to complete the *Initial Review Submission Form* (which is used for attachments), please address the association of this Protocol to an R&D Committee Project. This Protocol may represent a new R&D Project, or it may be an additional Protocol under an existing R&D Project (such as when a single grant supports multiple Protocols). Will this Protocol be submitted to the R&D Committee as a new Project?

Yes No

Section 29 - Existing Project Association

29) The associated R&D Project should already exist in the database. Identify the R&D Project(s) that correspond to this protocol.

Project Status	Proposal Number	Project Title	Principal Investigator
No Projects are Linked to this Study			

The Protocol Application is now complete for a Protocol attached to an existing Project.

Next you will go on to the Initial Review Submission Form. This form is used to collect the Application and any other needed attachments for submission to the IRB for review.

Press *Save and Continue*
